8.0 Drugs and Devices

8.1 * DRUGS AND/OR BIOLOGICS: Are you **STUDYING any drugs and/or biologics that are either approved or unapproved: **(REQUIRED)****

Yes No

8.2 LIST THE DRUGS/AGENTS: List the drugs or biologics that will be studied:

View Details	Drug Name	FDA Approved	A new drug or a new use of approved drug:	IND Number
	
Trade Drug Name: NAROPIN
 
Generic Drug Name: ROPIVACAINE HYDROCHLORIDE MONOHYDRATE
 
Investigational Drug Name:
	Yes	No	
	Trade Drug Name:	NAROPIN		
	Generic Drug Name:	ROPIVACAINE HYDROCHLORIDE MONOHYDRATE		
	Investigational Drug Name:			
	Identify the name of the manufacturer or source of investigational drug/biologic:			
	Is the drug supplied at no cost?	Yes		
	Is the Drug FDA Approved:	Yes		
	Is this a new drug or a new use of an already approved drug	No		

Is an IND necessary	No
IND Number	
Who holds the IND:	N/A
IND details:	
If FDA Approved and an IND is not required, Please provide a rationale for exemption:	
Are you currently using this IND in another research project?	No
If yes, list the IRB Number(s):	
Will the investigational pharmacy be dispensing?	No
If the source is not a FDA licensed facility, provide details regarding the purity, quality, stability and sterility of the investigational drug /biologic:	

	Trade Drug Name: FENTANYL Generic Drug Name: FENTANYL CITRATE Investigational Drug Name:	Yes	No	
--------------------------	---	-----	----	--

Trade Drug Name:	FENTANYL
Generic Drug Name:	FENTANYL CITRATE
Investigational Drug Name:	
Identify the name of the manufacturer or source of investigational drug/biologic:	
Is the drug supplied at no cost?	Yes
Is the Drug FDA Approved:	Yes
Is this a new drug or a new use of an already approved drug	No
Is an IND necessary	No
IND Number	
Who holds the IND:	N/A
IND details:	
If FDA Approved and an IND is not required, Please provide a rationale for exemption:	
Are you currently using this IND in another research project?	No
If yes, list the IRB Number(s):	
Will the investigational pharmacy be dispensing?	No
If the source is not a FDA licensed facility, provide details regarding the purity, quality, stability and sterility of the investigational drug /biologic:	

8.3 * MEDICAL DEVICES: Are you **STUDYING any medical devices, in vitro diagnostics, or assays that are either approved or unapproved: (REQUIRED)**

Yes No

8.6 * EXPANDED ACCESS: Is this an expanded access or compassionate use protocol, meaning the primary purpose is to diagnose, monitor or treat a patient's condition, rather than the collection of safety and efficacy data of the experimental agent or device: (REQUIRED)

Yes No

9.0 Sample Size and Eligibility Criteria

9.1 ENROLLMENT TARGET: How many people will you enroll:

120

If there are multiple participant groups, indicate how many people will be in each group:

9.3 SAMPLE SIZE JUSTIFICATION: Explain how and why the number of people was chosen. For multi-site studies, this is referring to the number that will be enrolled across all sites:

Based on labor analgesia literature, the median local bupivacaine dose per hour of analgesia was 10.5mg/hr with 95% confidence interval of 9.5 - 11.8mg/hr compared with continuous infusion group of 12.3mg/hr with 95% confidence interval of 10.5 - 14.0mg/hr. We expect similar effective size (0.6). With a power of 80% and accepting an alpha error of 0.05, we need 44 patients in each group.

In order to compensate for incomplete data collection, we estimated a total of 120 patients, 60 patients in each group should be enrolled.

9.4 * PARTICIPANT AGE RANGE: Eligible age ranges: (REQUIRED)

- 0-6 years
- 7-12 years
- 13-17 years
- 18-64 years
- 65+

9.5 * STUDY POPULATIONS: Data will be collected from or about the following types of people (check all that apply): (REQUIRED)

- Inpatients
- Outpatients
- Family members or caregivers
- Providers
- People who have a condition but who are not being seen as patients
- Healthy volunteers
- Students
- Staff of UCSF or affiliated institutions
- None of the above

9.6 * SPECIAL SUBJECT GROUPS: Check the populations that may be enrolled: (REQUIRED)

- Children / Minors
- Subjects unable to consent for themselves
- Subjects unable to consent for themselves (emergency setting)
- Subjects with diminished capacity to consent
- Subjects unable to read, speak or understand English
- Pregnant women
- Fetuses
- Neonates
- Prisoners
- Economically or educationally disadvantaged persons
- None of the above

9.7 INCLUSION CRITERIA: Briefly describe the population(s) that will be involved in this study. Include anyone that data will be collected from or about (e.g. patients, healthy controls, caregivers, providers, administrators, students, parents, family members, etc.):

Patients age 18 years of age or older, American Society of Anesthesia physical classification I - III, scheduled for abdominal surgery with epidural anesthesia as part of the perioperative treatment plan. Surgery at UCSF Mission Bay hospital.

9.8 EXCLUSION CRITERIA: List any exclusion criteria (e.g. reasons why someone would not be included in the study):

Age younger than 18 years of age, non-English speaking, contraindication for neuraxial anesthesia (such as, but not limited to coagulopathy, infection at site, allergy to local anesthetic), preexisting neurologic deficits, inability to consent due to cognitive dysfunction, patients with pain numeric rating score > 5 each day for greater than 3 months, daily opioid consumption > 100 oral morphine equivalents for 14 consecutive days prior to surgery, patient refusal.

9.9 * RESEARCH CONDUCTED ON PATIENT CARE WARDS: Do any study activities take place on patient care units: (REQUIRED)

Yes No

Attach a letter of acknowledgement for the study from the involved patient care manager. If you don't know who the patient care manager is, click [here](#) to send an email to the nursing group.

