4.0 Initial Screening Questions - Updated 2015

(Note: You must answer every question on this page to proceed.)

4.1 * PROJECT SUMMARY: (REQUIRED) Give a brief overview of this project (250 words or less). Tell us what this study is about, who is being studied, and what it aims to achieve. If you have an NIH Abstract, paste it here: Click on the orange question mark to the right for more detailed instructions.

Epidurals are an effective means for providing neuraxial anesthesia and analgesia. Prior studies in labor epidurals have demonstrated that a programmed intermittent bolus application of local anesthesia can improve pain control thus reducing the amount of local anesthetic required as well as improve patient

satisfaction when compared to continuous epidural infusions. The effects of programmed intermittent bolus of epidurals compared to continuous epidural infusions in a surgical setting have yet to be elucidated. Our goal is to evaluate the use of programmed intermittent bolus compared to continuous epidural infusion in a surgical patient population. We plan to enroll patients already undergoing surgery under the enhanced recovery after surgery (ERAS) pathways. ERAS pathway surgeries include colorectal, gynecologic, surgical oncology to name a few. The primary endpoints of the study will be the total local anesthetic consumption and total opioid consumption as surrogate markers for the quality of epidural anesthesia. Secondary endpoints are pain scores and functional measurements, patient satisfaction, and incidence of hypotension .

4.2 * HUD DEVICE: (REQUIRED) Does this application involve a Humanitarian Use Device (HUD):

- No
- Yes, and it includes a research component
- Yes, and it involves clinical care ONLY

4.3 * TYPE OF RESEARCH: (Click the Help link for definitions and guidance): (REQUIRED)

- Biomedical research
- Social, behavioral, educational, and/or public policy research
- Hybrid - includes aspects of BOTH types of research (check this option if your research is mainly social /behavioral but also involves specimen collection or blood draws to look at biological measures)

4.4 * SUBJECT CONTACT: (REQUIRED) Does this study involve ANY contact or interactions with participants:

- Yes (including phone, email or web contact)
- No (limited to medical records review, biological specimen analysis, and/or data analysis)

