As part of the UCSF Enhanced Recovery After Surgery (ERAS) pathway, all patients routinely treated with thoracic/lumbar epidural anesthesia for post-operative analgesia. The planned investigation does not change its approach, but compares solely two different modalities how epidural medications are administered. The study ends when the catheters are removed which is most often on post-operative day two, but can be later in case the patient may still benefit from epidural anesthesia. During the duration of the treatment with epidural anesthesia, enrolled patients will be randomized to receive either programmed intermittent bolus or continuous epidural administration of the local anesthetic ropivacaine (0.0625%) with fentanyl (2ug/ml). In addition to this maintenance administration of local anesthetic, the patient are also able to apply additional (demand) boluses of epidural medication by pressing a button. This technique, called patient- controlled epidural anesthesia (PCEA), is routinely used in all patients with epidural catheters and allows patients to receive additional medication in the event they experience discomfort. If the patients have still pain not covered by epidural anesthesia, they have access to additional RN-administered opioid pain medication. The normally used drugs for such treatment are oxycodone p.o. and hydromorphone i.v. However, other opioids could be used in this context and all opioid use would be quantified using a conversion to oral morphine equivalents. The primary outcomes of the study will be the total amount of local anesthetic administered and opioid requirements (oral morphine equivalents). Secondary outcomes are: numeric pain rating scores (should not be different as patients have access to additional analgesic medication), number of patient attempts to trigger additional PCEA boluses, overall patient satisfaction assessed through validated questionnaires, and incidence of hypotension.

7.5 BACKGROUND AND SIGNIFICANCE: Briefly provide the background and significance of this study (e.g. why is this study needed) (space limit: one half page):

If this is a first in humans study, please summarize the safety data from the animal studies. For pediatric drug or device studies, please identify if this is the first study in pediatric populations.

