12.0 Risks and Benefits

12.1 RESEARCH-RELATED RISKS: Check if your study involves any of these specific research-related risks

to participants that may need to be disclosed in the consent form:

- For interventional studies, risk that the regimen may be more harmful or less effective than other available interventions
- Risks associated with radiation exposure for imaging studies specifically for research purposes
- Risks associated with the administration of contrast agent for imaging studies
- Risks associated with withholding of treatment or discontinuation of current treatment (e.g., washout period is required by the study protocol)
- For randomized, placebo-controlled trials, possible temporary or permanent health consequences from the deprivation of effective therapies during the placebo administration period
- For studies involving a sham surgical procedure, the risk that participants may experience increased morbidity without the possibility of benefit
- Risks associated with modification or extension of a surgical procedure primarily for research purposes (e.g. risks associated with prolonging anesthesia, time in the operating room, etc.)
- Risk of pain or physical discomfort caused by the research intervention
- Possible personal discomfort due to sensitive topics (stress, embarrassment, trauma)

* For any boxes checked above, describe how you will minimize these risks and discomforts, e.g., adding or increasing the frequency of monitoring, additional screening to identify and exclude people with diminished kidney or liver function, or modification of procedures such as changing imaging studies to avoid giving contrast agent to people who are more likely to suffer side effects from it, etc.:

(REQUIRED)

Participants in the study have the risk that their study intervention (local anesthetic administration by bolus application or continuous infusion) results in inferior pain control. To ameliorate this risk we are firstly offering all patients the ability to obtain additional (demand) bolus administrations of local anesthetic and fentanyl through their epidural catheter. Secondly, all patients will have additional analgesics ordered in case they require additional pain control. We expect that all patients will be offered excellent pain control. For this reason, we did not choose pain scores as primary endpoint (we don't expect any differences here), but the need to administer additional analgesics.

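### The plan does not say whether a continued home opioid counts in the opioid primary outcome; if it does, precision is lost, by an amount the documents cannot fix

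*Combined protocol and SAP*

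**What the plan says.** **Eligibility.** Section 9.8 excludes patients with "daily opioid consumption > 100 oral morphine equivalents for 14 consecutive days prior to surgery". Both conditions must hold, so daily use at or below 100 OME is allowed, and so is higher use that did not last 14 days in a row. A separate criterion excludes "patients with pain numeric rating score > 5 each day for greater than 3 months".

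**The outcome, in three wordings.**
- Section 4.1 names as primary endpoints "total local anesthetic consumption and total opioid consumption as surrogate markers for the quality of epidural anesthesia".
- Section 7.4 first describes nurse-given opioid for pain that remains despite the epidural, usually oral oxycodone or intravenous hydromorphone. It adds that "other opioids could be used in this context and all opioid use would be quantified using a conversion to oral morphine equivalents" and then calls the outcome opioid requirements.
- Section 12.1 explains that pain scores were not chosen as the primary endpoint, "but the need to administer additional analgesics".

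**Analysis.** Section 7.25 plans an unpaired t-test for continuous variables and names no covariate. Section 7.9 describes block randomization and names no stratification factor. Section 9.3 derives the sample size from hourly bupivacaine dose in labor and gives no mean, SD or power for opioid use.

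No section says whether home opioid continues while the epidural runs, how it would be charted, or whether it would be counted.

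**The concern.** A patient's home opioid dose is set before randomization and says nothing about how well the assigned pump mode works. If it is continued and counted, it enters an outcome that section 4.1 reads as epidural quality. Oral oxycodone is a usual rescue drug, so a home oxycodone dose could not be told from rescue by drug or route alone. Someone abstracting the chart would have to choose between the total of 4.1 and the additional analgesics of 12.1 without guidance.

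At stake is the precision of one of two primary outcomes. Home dose can vary widely between patients, and the planned t-test does nothing to remove that variation, so a real difference in rescue need could be missed.

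**Working it through.** **1. The plan's own figure.** For effect size 0.6, two-sided alpha 0.05 and 80% power: n = 2(1.96 + 0.84)²/0.6² = 43.6, so 44 per group, as in section 9.3 (45 with the t distribution). This concerns local anesthetic dose and gives no guide to opioid use.

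**2. Assumptions, none of them in the documents.** Two-day rescue opioid is lognormal with mean 60 and SD 60 mg OME. The bolus arm has 40% less (mean 36, SD 36). There are 60 per arm. A share p of patients are home users with doses uniform on 10–100 mg/day, continued in full and counted for two days, which is 20–200 mg each.

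**3. Added variance.** Mean square of a uniform 20–200 mg dose: (200³ − 20³)/(3 × 180) = 14,800. Mean: 110. Variance added per patient = 14,800p − (110p)². Average rescue variance over the arms = (3600 + 1296)/2 = 2448. Halving all home doses to 5–50 mg/day divides the added variance by four.

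| Home users | Added variance, 10–100 mg/day | Relative to 2448 | Power, 10–100 mg/day | Power, 5–50 mg/day |
|---|---|---|---|---|
| none | 0 | 0 | about 81% | about 81% |
| 5% | 710 | 29% | about 67% | about 78% |
| 10% | 1359 | 56% | about 60% | about 74% |
| 20% | 2476 | 101% | about 47% | about 70% |

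Power is by simulation of the t-test; repeat runs differ by one or two points. With rescue mean and SD of 120 mg and home doses of 10–100 mg/day, power is about 78%, 74% and 69%.

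**4. A second model.** Take the plan's effect of 0.6 as applying to rescue opioid alone, with home doses uniform on 0–100 OME/day in a share f. Added daily variance = f × 100²/3 − (50f)². At f = 10% this is 333.3 − 25 = 308.3 (SD 17.6). The diluted effect is 0.6 × SD/√(SD² + 308.3), where SD is the daily rescue SD:
- SD 20: 0.451, power 56% at 44 per arm and 70% at 60.
- SD 30: 0.518, power 68% and 81%.
- SD 60: 0.576, power 77% and 88%.

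Over f from 5% to 30% and rescue SD from 20 to 60, power at 44 per arm runs from 38% to 79%, against 80% with no home opioid.

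**5. Chance imbalance.** Under the assumptions of step 2 with 10% users, the SD of the between-arm difference due to home opioid is √(2 × 1359/60) = 6.7 mg, against a true difference of 0.4 × 60 = 24 mg. The standard error includes this variation: with no true effect, simulated type I error stays close to 5%.

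**6. Subtracting the reported dose.** If home opioid was not in fact given, subtraction inserts the same variance with the opposite sign. Power is then about 67%, 57% and 48% at 5%, 10% and 20% users, as low as with counting.

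**The case against.** The strongest reply is that the plan already means rescue opioid. In 7.4 the conversion sentence follows the description of nurse-given opioid for uncovered pain and refers back to that context, so it most naturally covers all rescue agents. Section 12.1 speaks of additional analgesics and 10.13 of adjunct analgesics. Only the short summary in 4.1 says total. This largely stands: a reader might infer from 4.1, or from "all opioid use would be quantified using a conversion to oral morphine equivalents" taken alone, that the plan orders home opioid to be counted. Read together, the sections leave it undefined.

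It is also fair that the documents give no share of home users, no doses, no statement that home opioid continues and no opioid SD. The chronic-pain criterion may remove some heavy users, though it works on pain score and would not catch patients whose pain is controlled on opioids.

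A reader might further infer that a chance excess of home users in one arm could produce a false effect beyond the nominal error rate. It would not: allocation is randomized, and step 5 shows that the test already allows for such imbalance.

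What the reply does not remove is the conflict between total and additional in the description of a primary outcome, with no abstraction rule to settle it.

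**Conclusion.** The point holds as an undefined element of a primary outcome. Sections 4.1, 7.4 and 12.1 give different values for any patient whose home opioid is continued, and the eligibility rule admits such patients. If the 4.1 wording is followed with an unadjusted t-test, the outcome carries noise unrelated to pump mode.

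The size is conditional. Under the assumptions of step 2, power falls from about 81% to between 47% and 67% for 5% to 20% home users on 10–100 mg/day, and to between 70% and 78% on half those doses. There is practically no loss if home opioid is rare or low, and none if it is not continued. A general claim of large noise is therefore not supported by the documents.

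**What to change.** 1. In 7.4, define the opioid primary as opioid given in addition to any continued home regimen, with charted home-regimen doses not counted, and bring 4.1 and 12.1 into line.
2. Record the pre-operative daily dose in OME as a number at screening, where it already has to be assessed for the 9.8 criterion.
3. In 7.25, replace the plain t-test for this outcome with ANCOVA using that dose as covariate. This does not require assuming that the home dose was given.
4. Report total opioid as a secondary outcome.
5. Do not subtract the reported home dose, for the reason in step 6 of the working.

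The cost is a few sentences, one screening field and an abstraction rule. Some error in reported doses, or in classifying charted doses as home or rescue, will remain; it should be equal in both arms. The change concerns only what is counted and leaves clinical care untouched.

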10.0 Recruitment and Consent

10.1 * RECRUITMENT METHODS: What kinds of methods will be used to identify potential participants for recruitment (check all that apply): (REQUIRED)

- Medical records review
- Recruitment registry
- Re-contact of participants from the investigators' previous studies
- Referrals from colleagues (attach the 'Dear Colleague' letter or other recruitment materials you will provide to colleagues)
- Referrals from the community / word of mouth
- Advertisements (flyers, brochures, radio or t.v. ads, posting on clinical research sites or social media, presentation of the study at community events/media, etc.)
- Online recruiting tool such as TrialSpark
- CTSI Recruitment Services unit
- Other method (describe below)

* Provide details about the other recruitment methods: **(REQUIRED)**

We will plan to screen eligible patients based from their encounters with the anesthesia Prepare appointment as part of their preparation for upcoming surgery. We will recruit them at that time or contact them after they have been identified. Additionally, patients can also be identified by using the surgical scheduling board for specific procedures.

10.2 * SEARCHING OF MEDICAL RECORDS: (REQUIRED)

Whose patients are they:

- Investigators' own patients or patients seen within the same practice
- Patients not under the care of the investigators

How and by whom will records be accessed and searched (check all that apply):

- Self-search in APeX or other medical records source
- Self-search using UCSF's Research Cohort Selection Tool
- CTSI Consultation Service Recruitment Services
- UCSF Academic Research Services (ARS)
- University of California Research Exchange (UC ReX)
- Other method (describe below)

10.3 DETERMINATION OF ELIGIBILITY: How, when, and by whom will eligibility for recruitment be determined:

Eligibility will be determined after patients undergo a pre-operative anesthesia evaluation by a nurse practitioner or anesthesia provider prior to surgery. This appointment varies from a few days to a few weeks before the scheduled operation. Eligible patients will be identified by anesthesia providers involved in the study.

10.4 INITIATION OF CONTACT: Who initiates contact (check all that apply):

- Investigators/study team
- UCSF recruitment unit (e.g. CTSI Consultation Services)
- Potential participant

10.5 * HOW IS CONTACT INITIATED: (check all that apply): (REQUIRED)

- In person
- Phone
- Letter / email
- Website or app
- Other (explain below)

Attach the telephone recruitment script in the Other Study Documents section of the Initial Review Submission Packet Form. If potential participants will initiate contact, attach the telephone screening script that will be used to provide more information about the study and determine if callers are eligible to participate.

10.6 RECRUITMENT PLAN: Based on the checkboxes you chose above, please provide a narrative describing your recruitment plan. We want to know:

- Who is conducting the search for potential participants, and how?
- How are potential subjects being approached for recruitment? By whom, and when?

If there will be more than one participant group (e.g. patients, healthy controls, caregivers, family members, providers, etc.), provide details about the recruitment plans for each group. (Recommended length - 100-250 words)

Patients eligible for this study will be informed of the study by an anesthesia provider participating in the study after their initial pre-operative anesthesia evaluation, but prior to day of surgery. Patient who meet the inclusion and non-inclusion criteria will receive a phone call from one of the study investigators explaining the study prior to the day of surgery. The consent form will be offered to them via mail or e-mail prior to the day of surgery to allow ample time to review and consider the patient's participation in the study. On the day of surgery, information about the study will be reiterated by an anesthesia provider and all questions will be answered prior to randomization.

10.7 * CONSENT METHODS: How will permission to participate (i.e., informed consent) be obtained from each potential participant. If there will be multiple groups and different plans for consenting each, check all that apply. See the orange Help bubble to the right for more detailed guidance. Participants will (check all that apply): (REQUIRED)

- Sign a consent form at the end of the consent discussion (signed consent)
- Provide online 'eConsent' using DocuSign or another E-Signature system
- Click through a link in a survey or email after reading about the study and then complete the study online (electronic consent)
- Be told about the study and be given a handout/information sheet and be asked if they agree to participate (verbal consent)
- Complete the study activities and turn in materials, as in the case of a completed survey that is placed in a drop box or mailed to the study team (implied consent)
- Not be able to provide consent and will have a family member consent for them, as in the case of a critically ill or unconscious patient (surrogate consent)
- Not be able to provide consent (emergency waiver of consent - allowed for minimal risk research or greater than minimal risk research with an approved community consultation plan)
- Not know about the study, as in the case of chart reviews or observations of public behavior (waiver of consent)
- Other method (describe below)

Attach your consent form, information sheet, or electronic consent text in the Informed Consent Documents section of the Initial Review Submission Packet Form.

10.8 * CONSENT PROCESS: Describe the process for obtaining informed consent, including details such as who will have the consent discussion and when participants will be asked to sign the consent form in relation to finding out about the study. For online and electronic consent, explain that process in detail: (REQUIRED) If there are multiple groups being consented differently, provide details about the consent process for each group. If you are relying on verbal or implied consent, provide details about how that will happen. We encourage researchers to review [UC Irvine's excellent guidance on obtaining informed consent](#).

Potential patients meeting the inclusion/non-inclusion criterias will be contacted via telephone prior to their day of surgery by a member of the research team. At this time, the research team will introduce themselves, confirm the surgery type and surgery day and any other clarifying information regarding the patient's past medical information as it is relevant to the study. If there are no contraindications for the patient for the study, the patient will be introduced to the study. We will discuss the study's goals, risks and benefits. If the patient agrees to be a participant, the research team will offer to send them a consent via mail or email prior to the date of surgery. A formal written consent will be obtained the day of surgery.

Potential study participatnets will be introduced to the study after their routine pre-operative anesthesia evaluation verbally. They will also be offered a written copy of the consent form via mail or email prior to the day of surgery. This consent form includes the name and contact information of the study investigator. On the day of surgery, an anesthesia attending will review this information, answer any questions, and assure that there is a written consent prior to randomization.

* It is important that the people obtaining consent are qualified to do so. Briefly describe the training and experience these individuals have in obtaining informed consent: **(REQUIRED)**

All study personnel involved in the enrollment process have prior experience in enrolling patients for clinical studies. They are either fully trained, board certified anesthesiologists, anesthesia residents involved in the design of this study ([name]), or study coordinators currently enrolling patients in other ongoing clinical studies done by our department.

10.9 * CONSENT COMPREHENSION: Indicate how the study team will assess and enhance the subjects' understanding of study procedures, risks, and benefits prior to signing the consent form (check all that apply): (REQUIRED) Tip: Review the Consent Comprehension - Learning Notes in the Help bubble at the right for specific questions that can be asked to assess comprehension, consider using UCSD's Brief Assessment of Capacity to Consent (UBACC), and review UC Irvine's guidance on Subject Consent Assessment for more detail on how to conduct the assessment.

- The study team will engage the potential participant in a dialogue, using open-ended questions about the nature of the study or the experimental treatment, the risks and benefits of participating, and the voluntary nature of participation
- Potential participants will be asked or shown a series of questions to assess their understanding of the study purpose, procedures, risks and benefits, as well as the voluntary nature of participation (especially appropriate when the consent process happens online or through a mobile health app)
- Other method (describe below):

10.13 TIME: What is the estimated time commitment for participants (per visit and in total):

IMPORTANT TIP: Ensure this information is consistent with the information provided in the consent form.

An initial phone call to the patient to introduce the study to the patient will take approximately 10 minutes. We will offer the informed consent form to eligible patients via mail or e-mail prior to the day of surgery. On the day of surgery, additional time may be allotted if needed to answer any additional questions from the patient. Epidural placement will follow pre-established ERAS protocol as per institution guidelines and should not disrupt the current work flow of the perioperative setting. Follow up with regards to pain scores, hypotension, amount of adjunct analgesics will be obtained via chart biopsy. Patient satisfaction will be obtained at the time of discontinuation of the epidural, which should take approximal 5 minutes. Total face-time will be approximately 15 minutes. Epidurals are removed typically on the morning of post-operative day 2, however some may be removed earlier or later pending clinical scenario.

